**TRANSEPIDERMAL DELIVERY OF TRIAMCINOLONE
ACETONIDE OR PLATELET RICH PLASMA USING
EITHER FRACTIONAL CARBON DIOXIDE LASER OR
MICRONEEDLING IN TREATMENT OF
ALOPECIA AREATA**

May 2019

INTRODUCTION

Alopecia areata (AA) is one of the most common forms of non-scarring alopecia involving the scalp and/or body.⁽¹⁾ Estimated incidence of alopecia areata is 20.9 per 100,000 person-years with a cumulative lifetime incidence of 2.1%.⁽²⁾

The exact pathophysiology of alopecia areata remains unknown. The most widely accepted hypothesis is that alopecia areata is a T cell-mediated autoimmune condition that is most likely to occur in genetically predisposed individuals.⁽³⁾

Alopecia areata can be classified according to its pattern, as follows: patchy, reticular, ophiasis, alopecia totalis and alopecia universalis.⁽⁴⁾

Although, alopecia areata is a benign condition and most patients are asymptomatic, it can cause emotional and psychosocial distress in affected individuals.⁽⁵⁾

First-line therapies include intralesional corticosteroids, topical corticosteroids, minoxidil, anthralin, topical immunotherapy, prostaglandin analogues, topical retinoids bexarotene, and capsaicin.⁽⁶⁾ Second- and third-line treatments include topical and systemic immunomodulatory therapies such as oral and topical psoralen plus UVA radiation and photodynamic therapy.⁽⁷⁾ No treatment is either curative or preventive.⁽⁸⁾ Since no single treatment option is certain to treat alopecia areata, the need for new therapies is mounting.

Intralesional corticosteroids, most commonly triamcinolone acetonide are considered a first-line treatment method for limited disease and can be used as adjunctive therapy in extensive disease.⁽⁹⁾ Because triamcinolone is only

emulsified temporarily to the water, usually it is delivered by the painful intralesional injection.⁽¹⁰⁾

Platelet-rich plasma (PRP) has emerged as a new treatment modality in dermatology, and preliminary evidence has suggested that it might have a beneficial role in hair growth.⁽⁸⁾

Drugs applied topically have the advantage of fewer side effects and bypassing the first-pass effect.⁽¹¹⁾ However, transepidermal dermal drug delivery has limitations, including decreased penetration of larger and water-soluble molecules.⁽¹²⁾ Only lipophilic and smaller than 500Da molecules are capable of penetrating an intact stratum corneum. Furthermore, only 1% to 5% of the product applied to the skin is absorbed and becomes bioavailable to exert its therapeutic effect.⁽¹³⁾ In addition, the stratum corneum acts as a barrier that limits the penetration of substances through the skin.⁽¹⁴⁾

Several strategies have been used to improve many drug penetrations into the skin: microneedling, ultrasound, and more recently transepidermal drug delivery (TED). TED is a technique based on applying a medication following an ablative method (CO₂ laser, erbium lasers or ablative radiofrequency), which create vertical channels to assist the delivery of topically applied drugs into the skin. The use of nonablative lasers as well as microneedling technique has been reported with the same purpose.⁽¹⁴⁾

Fractional laser-assisted drug delivery of corticosteroids for resistant alopecia areata is a new concept in dermatological therapy.⁽¹⁵⁾ Lasers stimulate drug delivery by the means of three processes: tissue ablation, which removes the stratum corneum and the most superficial layers of the epidermis; photomechanical waves, resulting from the conversion of light into mechanical energy; and non-ablative resurfacing, where thermal and physical injuries rupture the skin barrier, promoting the delivery of medications.⁽¹⁶⁾

Microneedle devices, such as Dermaroller and Dermapen, are minimally invasive devices that bypass the stratum corneum barrier, thus accessing the skin microcirculation and achieving systemic delivery by the transepidermal route.⁽¹⁷⁾ They create transient aqueous microchannels in the stratum corneum, that vary from 0.5 to 2.5 mm. Subsequently, a conventional, topically applied drug formulation can permeate through these microchannels via passive diffusion.⁽¹⁸⁾

Trichoscopy, hair and scalp dermoscopy, is a fast, non-invasive method useful in the diagnosis and therapeutic monitoring of scalp and hair diseases.⁽¹⁹⁾ The trichoscopic features of alopecia areata were first described in 2004.⁽²⁰⁾ The reported features of alopecia areata are: yellow dots (6–100% patients), short vellus hairs (34–100%), black dots (0–84%), broken hairs (0–71%) and exclamation mark hairs (12–71%). The diagnosis should be based on the coexistence of several trichoscopic findings, not on the presence of a single feature.⁽¹⁹⁾

AIM OF THE WORK

The aim of this study is to evaluate the use of fractional carbon dioxide laser versus microneedling in the transepidermal delivery of triamcinolone acetonide and platelet rich plasma in treatment of alopecia areata.

PATIENTS

This study will be carried out on sixty patients, of either sex, presenting with alopecia areata to the outpatient clinic of Dermatology, Venereology and Andrology, Alexandria University Hospitals, after approval of the local Ethical Committee and having an informed written consent from every patient included in the study, or his/her legal guardian in case of children.

Inclusion criteria:

1. Patients with alopecia areata of either gender, diagnosed both clinically and by trichoscopy
2. Patients not responding to treatment (topical and/or systemic), used properly and regularly, for at least 3 months duration

Exclusion criteria:^(8, 21-23)

- 1- Alopecia areata with evidence of spontaneous hair regrowth
- 2- Patients having active scalp inflammation or other scalp or hair diseases
- 3- Pregnant and lactating women
- 4- Patients with any bleeding disorder or receiving anti-coagulant therapy
- 5- Immunocompromised patients

METHODS

History will be obtained at baseline according to the guidelines of the National Alopecia Areata Foundation including:^(8, 15, 21, 24)

- Patient demographics (name, age, sex, address, contact number, . . .)
- Hair loss: age of onset, total duration of disease, number of relapses, family history
- Onset and duration of hair loss of the present episode, and number of aa patches
- Associated symptoms,
- Any history of previously received treatment for the hair loss,
- History of bleeding tendencies, or intake of any anticoagulant drugs
- History of any medical or autoimmune disease

Clinical evaluation:^(15, 21, 24)

The clinical evaluation of alopecia areata will be made in accordance with the guidelines of the National Alopecia Areata Foundation.⁽²⁴⁾ Under adequate illumination, patient will be examined for:

- The pattern of hair loss
- Number of patches
- Skin changes over the affected area
- Baseline SALT score ⁽²⁴⁻²⁶⁾
- Any associated nail changes
- Also the patient will be thoroughly assessed for any associated autoimmune and endocrine disorders with relevant history, physical examination, and investigations wherever indicated.

Trichoscopic/Dermoscopic evaluation : (25, 27, 28)

Trichoscopic evaluation will be performed using a DermLite® IV (3 Gen, San Juan Capistrano, CA, USA), which can be used without immersion gels because of the presence of polarizing filters. The dermoscopic/trichoscopic features of the alopecic patch(es) will be noted.

Patients will be randomly allocated, by closed envelope method , into one of four equal groups, fifteen patients each:

Group I :Fractional Carbon dioxide laser (CO₂ Laser) and triamcinolone acetonide (TrA; 10 mg/ mL).

Group II: Microneedling with Dermapen and triamcinolone acetonide (TrA; 10 mg/ ml).

Group III: Fractional Carbon dioxide laser (CO₂ Laser) and Platelet-rich plasma (PRP)

Group IV: Microneedling with Dermapen and Platelet-rich plasma (PRP)

Each patient will receive four treatments, with an interval of three weeks between the treatment sessions, for a total of 12 weeks. (14, 21, 29) This will be followed by a follow up period of another 4 weeks. The patients will be given no topical treatments for the alopecia areata in between the sessions. Topical post-procedure care in the form of topical antibiotics, emollient or sunscreen may be used.

Group I:Fractional Carbon dioxide laser (CO₂ Laser) and triamcinolone acetonide (TrA; 10 mg/ ml) (14, 15)

The ablative fractional CO₂ laser is delivered to the patients' scalp.

The fractional ablative method is applied immediately before the topical medication.

Laser treatment will be given to the affected area, and immediately after the treatment, triamcinolone solution (10 mg/ml) will be dropped on the treated area and spread evenly.

Group II: Microneedling with Dermapen and triamcinolone acetonide (TrA; 10 mg/ ml) (29-32)

Microneedling is performed using Dermapen.

This creates pin point bleeding or mild erythema which will be considered as the end point.

Triamcinolone acetonide in concentration of 10 mg/ml (0.1 ml containing 1 mg of triamcinolone) will be applied on each lesion twice, before and after performing microneedling.

Group III: Fractional Carbon dioxide laser (CO₂ Laser) and Platelet-rich plasma (PRP)⁽³³⁾

The same laser parameters as group I will be used, followed by application of freshly prepared PRP. The applied PRP will be spread over the whole affected area.

Group IV: Microneedling with Dermapen and Platelet-rich plasma (PRP)^(21, 29-32)

Microneedling using dermapen is performed as Group II.

Microneedling is preceded and followed by intermittent application of freshly prepared PRP. The applied PRP will be spread over the whole affected area and again rolled till pinpoint bleeding points are noticed.

Assessment criteria:^(21, 24)

Each patch will be digitally macrophotographed, and evaluated clinically and by dermoscopy at baseline and at the end of the study, for signs of hair regrowth.

Other criteria that will be evaluated:

- Patient's satisfaction
- Any complications, side effects clinically and using a dermoscope
- Ease of the technique
- Cost

ETHICS OF RESEARCH

Research on human or human products:

- Prospective study: Informed consent will be taken from patients. In case of incompetent patients the informed consent will be taken from the guardians.
 - Retrospective study: Confidentiality of records will be considered
 - DNA / genomic material: Informed consent for DNA / genomic test and for research will be taken from patients. No further tests will be carried out except with further approval of committee and patients. If the samples will travel outside Egypt the researcher will be responsible for transportation and security approval.
 - All drugs used in the research are approved by the Egyptian Ministry of Health
-

Research on animal:

- The animal species are appropriate for the test.
- After test, if the animal will suffer, it will be euthanized and properly disposed.
- After operation, it will have a proper postoperative care.

RESULTS

The results obtained from this study will be tabulated and statistically analyzed using the standard statistical methods.

DISCUSSION

The results obtained from this study will be discussed in view of achievement of the aim and compared with any available published data in the same field of the research.

REFERENCES

1. Seetharam KA. Alopecia areata: an update. *Indian J Dermatol Venereol Leprol.* 2013;79(5):563-75.

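### Does allocating 60 patients to four groups of 15 force the laser versus microneedling question to be answered with 15 against 15?

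*Protocol*

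**What the plan says.** The section AIM OF THE WORK says that the study will "evaluate the use of fractional carbon dioxide laser versus microneedling in the transepidermal delivery" of two products, triamcinolone acetonide and platelet-rich plasma. The section PATIENTS sets the size: "This study will be carried out on sixty patients, of either sex". Under METHODS, patients are allocated by closed envelope "into one of four equal groups, fifteen patients each". Groups I and II receive triamcinolone, with laser and with microneedling respectively. Groups III and IV receive platelet-rich plasma, again with laser and with microneedling respectively.

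On analysis, the RESULTS section says only that the results will be "tabulated and statistically analyzed using the standard statistical methods". The protocol does not use the word factorial. It names no main effect, interaction, pairwise test or omnibus test, and gives no significance level, power or effect size.

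**The concern.** Two devices crossed with two products in equal cells make a balanced 2x2 factorial, but the protocol lists the cells simply as four groups. A reader may expect the usual treatment of four groups: an overall test followed by up to six pairwise comparisons. Two of those six pairs (I with IV, II with III) change device and product together and isolate neither. Each pair that does isolate the device uses only 30 of the 60 patients.

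If that were the plan, the device comparison would lose precision, and six unadjusted tests would inflate the false-positive rate. A single device contrast on all 60 patients would avoid both at no cost in recruitment.

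**Working it through.** **Inputs from the protocol.** Total 60; four groups of 15, and 4 × 15 = 60 agrees. Laser is groups I and III, 15 + 15 = 30. Microneedling is groups II and IV, 15 + 15 = 30.

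**Assumptions, because the protocol gives no figures.** Two-sided 5% level, 80% power for detectable differences, a normally distributed outcome measured in SD units, no dropout.

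**Step 1: precision under each layout.** The standard error of a difference is SD × √(2/n).
- 15 against 15: √(2/15) = 0.365 SD.
- 30 against 30: √(2/30) = 0.258 SD.
- Ratio 0.258/0.365 = 0.71, so pooling halves the variance. This ratio needs no assumed effect size.

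**Step 2: detectable difference at 80% power.** The normal approximation is (1.960 + 0.842) × √(2/n): 1.02 SD for n = 15 and 0.72 SD for n = 30. With the noncentral t distribution the values are 1.06 and 0.74 SD.

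**Step 3: power at an assumed device effect of 0.75 SD, the same for both products (noncentral t or F).**

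| Analysis | Power |
|---|---|
| One pair, 15 against 15 | 51% |
| One pair, Bonferroni over six | 24% |
| Omnibus F test on 3 and 56 df | 65% |
| Pooled device contrast, 30 against 30 | 81% |

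Six unadjusted pairwise tests give about a 20% chance of at least one false positive when no groups differ (simulation).

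The arithmetic behind the concern is therefore right. What remains is whether the protocol commits to the weaker analysis, and whether the stronger one is clearly better.

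**Step 4: what the text commits to.** The allocation sentence assigns patients and does nothing more. The RESULTS sentence names no test. A two-way analysis of variance or a regression with device and product terms is a standard method, so the pooled contrast lies within the wording. The 15-against-15 comparison and the six tests are inferences about an analysis that the protocol does not describe.

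**Step 5: whether the allocation harms the pooled analysis.** It does not. Equal cells make device and product orthogonal, so the 30-against-30 contrast is available without any change to the design.

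**Step 6: what pooling depends on.** Suppose the device effect is 1.0 SD with one product and 0 with the other. The pooled effect is (1.0 + 0)/2 = 0.5 SD.
- Power of the pooled contrast: 48% (noncentral t; 49% by the normal approximation).
- Power of the 15-against-15 test within the responsive product: 75% (78% by the normal approximation).

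The interaction has standard error SD × √(4/15) = 0.516 SD, so its detectable size at 80% power is 2.802 × 0.516 = 1.45 SD. Sixty patients can hardly check the condition that pooling needs.

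**Step 7: a fairer comparison for the within-product reading.** Only two pairs address the device (I with II, III with IV), so a correction over six charges that question for four irrelevant tests. At 0.75 SD in both products, the chance that at least one of the two is significant is 1 − (1 − 0.509)² = 76% unadjusted. With Bonferroni over two, each test has 39% power, and the chance of at least one is 1 − (1 − 0.390)² = 63%. These are chances of at least one significant result, not of both: both unadjusted tests are significant with probability 0.509² = 26%.

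**The case for a change.** The best argument for keeping the concern is that the choice of groups to compare is a matter of design, not of analysis detail. It decides whether 60 patients supply 15 or 30 per side, and a protocol that states an aim should link it to its groups. Left open, the choice could be made among six comparisons after the data are seen. One or two sentences would settle it, with no extra patients.

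Some of this stands. The protocol does not name the factorial structure or its device contrast, and if the groups were compared pairwise, each device comparison would rest on 15 against 15. But that is an absence of detail, and the detail is of a kind that a statistical analysis plan commonly supplies. It is not a wrong statement, a contradiction or a bad choice fixed in the text.

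Nor does the aim dictate pooling. It can be read as one device comparison over both products or as a device comparison for each product; on the second reading, I against II and III against IV are the direct contrasts. The INTRODUCTION says that penetration depends on molecular size and solubility, so a device effect that differs by product is plausible.

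The contrast would also carry more than the device. The laser groups receive the product after the procedure, the microneedling groups before and after it. This applies equally within each product, so it favours neither analysis, but pooling does not isolate the device either.

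**Conclusion.** The concern does not hold. The four groups do form a balanced 2x2 layout, and the calculations are correct: 1.06 against 0.74 SD detectable, and 51% against 81% power at 0.75 SD. But they describe a loss that would arise only under an analysis the protocol does not state. The allocation is correct for a pooled device contrast, and the analysis sentence permits one. The contrast, model terms and multiplicity handling are left unstated, which is not an error in a protocol read without its statistical analysis plan.

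The choice between pooled and within-product comparisons is also a trade-off. Pooling wins when the device effect is similar for both products. It loses, 48% against 75%, when an effect of 1.0 SD is confined to one of them. An interaction below about 1.45 SD would probably go undetected. All power figures rest on the assumed two-sided 5% level, a normal outcome, no dropout and the assumed effect sizes; only the standard-error ratio of 0.71 is independent of the assumed effect.

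### The only rule on other alopecia treatment covers topical products between sessions; intralesional and systemic treatment is never barred, and the topical bar lapses before the final regrowth reading

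*Protocol*

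**What the plan says.** The restriction stands in the Protocol, Methods, in the paragraph on the treatment schedule after the four groups are listed: "The patients will be given no topical treatments for the alopecia areata in between the sessions". The sentence after it only permits supportive care: "Topical post-procedure care in the form of topical antibiotics, emollient or sunscreen may be used". No other sentence restricts alopecia treatment during the study.

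The same paragraph sets the schedule: "Each patient will receive four treatments, with an interval of three weeks between the treatment sessions, for a total of 12 weeks", and then "This will be followed by a follow up period of another 4 weeks". Under Assessment criteria, each patch is evaluated "at baseline and at the end of the study, for signs of hair regrowth". No intermediate regrowth reading is listed, and no week number is given for session 4 or for the final reading.

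Two other places bear on the scope of the rule. The Introduction states: "Intralesional corticosteroids, most commonly triamcinolone acetonide are considered a first-line treatment method for limited disease". The second inclusion criterion is "Patients not responding to treatment (topical and/or systemic), used properly and regularly, for at least 3 months duration", with no stop date or washout. Treatment history appears in the list of items obtained at baseline: "Any history of previously received treatment for the hair loss".

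**The concern.** The protocol chose to restrict other treatment, but fixed the restriction to one route and to a period that, taken literally, ends before the outcome is read.

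The route matters more. The trial compares triamcinolone with PRP, each delivered by laser or by microneedling. The protocol itself names injected triamcinolone as standard treatment, and its entrants have already failed other treatment, so they have reason to look for more. A patient in group III or IV who was injected with triamcinolone would have received the comparator's drug, and no sentence in the protocol forbids it. A patient already on systemic treatment at entry is not told to stop.

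At stake is the attribution of regrowth. There is one post-treatment reading, so regrowth helped by outside treatment would be credited to the allocated combination. With 15 patients per group, one patient is 1/15 = 6.7% of a group, so a few such patients could be visible in a group's result.

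**Working it through.** **Scope, by setting the texts side by side.**

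| Route | Barred between sessions? | Barred from session 4 to the final reading? |
|---|---|---|
| Topical alopecia treatment | Yes | Not on the literal wording |
| Intralesional, including triamcinolone | No | No |
| Systemic | No | No |

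The exclusion criteria do not fill the empty cells. The only drug class they name is anticoagulants. The exclusion of immunocompromised patients describes a state at entry; it might keep out some people on systemic immunosuppressants, but it names no alopecia drug, does not govern treatment started later, and does not touch intralesional steroid. The scope gap therefore holds on every reading of the schedule.

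**Window, by arithmetic.** Inputs from Methods: 4 sessions, 3 weeks apart, 12 weeks in total, then 4 weeks of follow-up.

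1. The plan's own figure: 4 sessions × 3 weeks = 12 weeks. This reproduces the stated total if the 3 weeks after the last session are counted.
2. First to last session: (4 − 1) intervals × 3 weeks = 9 weeks, with sessions at weeks 0, 3, 6 and 9. Time between sessions, taken literally, ends at week 9.
3. End of study on the plain reading: 12 + 4 = week 16.
4. Gap = week of final reading − week at which the bar ends = 16 − 9 = **7 weeks**.

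Other readings shorten the gap:

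- Bar taken to run to week 12, reading at week 16: 16 − 12 = 4 weeks.
- Follow-up counted from session 4, reading at 9 + 4 = week 13: 13 − 9 = 4 weeks.
- Bar ends at week 9, reading at week 12: 12 − 9 = 3 weeks.
- Bar runs to week 12 and reading at week 12: 12 − 12 = 0 weeks.

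The last two place the final reading before the follow-up that Methods says comes after treatment, so they are the less natural ones. These readings are not equally plausible and should not be counted as votes. The 7-week figure follows from the literal wording.

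**Effect on the comparison.** No calculation is possible. The document gives no rate of outside treatment and no response rate for it.

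**The case against.** The strongest reply is that silence is not permission. Methods sets out one allocated combination per patient, then a follow-up in which no further therapy is planned. A triamcinolone injection in a PRP group would depart from that regimen, and most clinicians would see this. It is fair that nothing in the text provides for such treatment, and a reader should not infer that the protocol allows crossover by design. But the protocol does contain an explicit restriction, and naming topical products alone invites the reading that other routes are left to judgement.

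A second reply concerns weight. The inclusion criterion uses at least 3 months (about 13 weeks) of treatment to judge non-response, whereas the longest topical gap is 7 weeks, and patients who had failed topical treatment would be returning to a class that had not worked. This stands as a reason not to lead with the topical window. It does not rule out an effect, and it does not answer the point about injections.

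Third, the rule is the same in all four groups, so no built-in imbalance is shown. That also stands. Differential use is possible, since patients without regrowth have the most reason to seek help, but the document offers no evidence of it.

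Two stronger inferences are tempting and are not supported. One is that outside use would go unseen. Patients return every three weeks through session 4 and are evaluated again at the end, and the case record form is not shown, so the text supports only that later recording is not specified. The other is that the wording about what patients are given covers only what the clinic supplies and leaves their own use free. That is one narrow reading of ordinary language and identifies no error.

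Permitted and prohibited treatment is a protocol matter, so a statistical analysis plan would not cure this: it cannot prevent the use, or adjust for use that was never recorded.

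**Conclusion.** The point holds as a conduct rule fixed too narrowly. Intralesional and systemic alopecia treatment is unrestricted for the whole study, whichever way the schedule is read. The topical bar, on its literal wording, stops about 7 weeks before the final regrowth reading; this assumes session 1 at week 0, session 4 at week 9 and the reading at week 16, and other readings give a smaller gap, down to none.

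The consequence is possible contamination of the group comparison. A reader might go further and conclude that the comparison is biased toward or away from a particular group; the document does not support that, because neither size nor direction can be derived from it. The amendment is worth making because it is cheap and because only the protocol can control this.

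**What to change.** Replace the sentence in Methods with: *From baseline until the final regrowth reading, patients in all four groups will receive and use no treatment for alopecia areata (topical, intralesional or systemic) other than the allocated sessions.* Keep the sentence permitting post-procedure antibiotics, emollient or sunscreen. State the week of the final reading (week 16, if 12 + 4 is meant), so that the end of the restriction is unambiguous. Record any other alopecia treatment used after baseline, with its start date. How such patients are handled in the analysis can be left to the statistical analysis plan.

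The cost is one amended sentence and one line on the case record form, with no extra visits or patients. The downside is that patients without regrowth wait a few more weeks before trying something else.

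### Group II needling may stop at mild erythema, but Group IV, said to be needled the same way, must reach pinpoint bleeding on a repeat pass, so needling intensity can differ between the two drugs

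*Protocol*

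**What the plan says.** All of this is in the Methods section of the protocol, in the paragraphs describing the four groups.

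- **Group II (microneedling, triamcinolone).** On the needling: "This creates pin point bleeding or mild erythema which will be considered as the end point". The drug "will be applied on each lesion twice, before and after performing microneedling". No second needling pass is described.
- **Group IV (microneedling, PRP).** The paragraph opens with a cross-reference: "Microneedling using dermapen is performed as Group II". It continues: "Microneedling is preceded and followed by intermittent application of freshly prepared PRP". It ends: "The applied PRP will be spread over the whole affected area and again rolled till pinpoint bleeding points are noticed".
- **Group III (laser, PRP), for contrast with Group I.** "The same laser parameters as group I will be used". No additional laser pass is added for PRP.
- **Schedule, all groups.** "Each patient will receive four treatments, with an interval of three weeks between the treatment sessions". There are fifteen patients in each group.

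**The concern.** The cross-reference shows that the authors meant needling to be the same for both drugs, as they did for the laser. The closing sentence of the Group IV paragraph undoes this by adding a requirement that Group II does not have.

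Needling intensity is not incidental here. The Introduction explains that microneedling works by opening channels through which the applied drug then passes, so the amount of needling is part of the delivery being tested. If the needling rule changes with the drug, a difference between Groups II and IV could come from the drug, from the needling, or from both. Drug and rule coincide completely in these two groups, so no later analysis could separate them.

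The same applies to asking whether the laser-versus-microneedling difference is alike for triamcinolone and PRP. A required repeat pass to bleeding could also plausibly bear on complications, patient satisfaction and ease of technique, all of which the Assessment criteria list.

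**Working it through.** The protocol gives no figure to reproduce. The check sets the two needling descriptions side by side, counts the exposure, and traces which contrasts are touched.

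**1. The two descriptions**

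| | Group II (triamcinolone) | Group IV (PRP) |
|---|---|---|
| Drug around needling | Before and after | Before and after, intermittently |
| End point of the needling step | Bleeding or mild erythema | As Group II, by cross-reference |
| Further pass after the drug is spread | None described | Yes |
| End point of that pass | Not applicable | Pinpoint bleeding only |

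Nothing elsewhere in the protocol gives Group II a second pass or allows Group IV to finish at erythema.

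**2. Exposure**

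- Sessions per needling group: 15 patients × 4 sessions = 60. Over two groups: 2 × 60 = 120.
- Sessions permitted to end at erythema: 0 to 60 of 60 in Group II, 0 of 60 in Group IV.
- At the lower end of the Group II range (every session happens to reach bleeding), the end points match and only Group IV's repeat pass differs.

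**3. Which contrasts are touched**

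Write I, II and III for the mean outcomes in those groups, and IV* for the mean that Group IV would have under Group II's needling rule. Let d be the unknown shift, possibly zero, caused by Group IV's rule, so that the observed mean is IV = IV* + d.

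- Drug contrast under needling: II − IV = (II − IV*) − d. It carries d.
- Difference in device effect between drugs: (II − I) − (IV − III) = [(II − I) − (IV* − III)] − d. It carries d.
- Device contrast with triamcinolone: II − I. No d.
- Device contrast with PRP: IV − III. It compares laser with needling under Group IV's single rule, so two rules are not mixed.
- Drug contrast under laser: I − III. No needling is involved and the laser parameters are common.

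**The case against.** Four points can be made on the other side.

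*The stated aim is spared.* The Aim of the Work is laser versus microneedling for delivering the two drugs, most directly I v II and III v IV. Neither mixes needling rules, and the protocol does not name II v IV as a planned comparison. This stands and limits the importance of the point. Even so, a four-group layout crossing two devices with two drugs invites both II v IV and the comparison of device effects across drugs.

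*The repeat pass may not be a separate pass.* The last Group IV sentence could describe needling and intermittent PRP alternating within one procedure until the visible end point. This is possible, although the wording favours a further pass. On that reading the gap narrows but does not close: erythema is enough in Group II and not in Group IV.

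*The difference may be deliberate.* Group IV cites an additional source, whose title concerns microneedling with PRP in alopecia areata, and the groups may be meant as drug-specific packages. That source cannot be consulted here. The explanation also sits badly with the protocol's own statement that Group IV is needled like Group II.

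*No harm is shown.* Nothing in the protocol shows that bleeding rather than erythema, or one more pass, alters regrowth. That is correct: the case rests on an avoidable ambiguity, not on a demonstrated bias.

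**Conclusion.** The point holds. As written, Groups II and IV are declared to be needled alike and then given different rules, and nothing in the protocol reconciles them. The drug comparison among needled patients, and the comparison of device effects between drugs, each carry the unknown shift d. The within-drug comparisons of laser with microneedling do not mix the two rules.

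The size of d is not computable and may be zero. What can be bounded is the exposure: up to 60 of 60 Group II sessions may stop at erythema, against none in Group IV. This assumes that operators follow the text, and that the closing Group IV sentence sets a requirement and does not merely describe what usually happens. The change should be made, because it removes a confounder that analysis cannot repair. It does not threaten the main aim.

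**What to change.** State one needling procedure for both microneedling groups at every session:

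- the same end point, for example pinpoint bleeding in both;
- the same number and order of needling passes around drug application, either giving Group II the repeat pass or removing it from Group IV;
- the same Dermapen setting, which the existing cross-reference already covers on its face and which needs only to be kept.

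Record the end point reached at each session, so that adherence to the common rule can be shown. Another common rule would serve as well; what matters is that it is shared.

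The cost is a wording change in two paragraphs and one tick-box at each of 120 sessions, with no extra patients or visits. The drawbacks are slightly less freedom for the operator and, if bleeding is chosen, further needling in some Group II sessions that would otherwise have stopped at erythema.
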